#### Exploratory outcome measures

- 1) Other Alcohol use measures, as measured by the TLFB, including Heavy Drinking Days, Drinks/ Day, and percent days abstinent.
- 2) Alcohol craving—as measured by the OCDS.
- 3) Sleep disturbance—as measured by the MOS-Sleep
- 4) Anxiety symptoms—as measured by the HAM-A

#### **Hypotheses testing:**

- 1) **Primary Hypothesis:** The mean maximum tolerated dose and mean adverse symptoms count will be calculated.
- 2) **Secondary Hypotheses:** Paired-samples T tests will be used to compare baseline assessments to end-of-study assessments for continuous variables (e.g., craving or withdrawal scores) and the chi-square test will

---

be used for variables reported as proportions (e.g., percent days abstinent, proportion heavy drinking days).

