## **Description of Subject Population**

### **Sample #1**

Specify subject population

Adults with AUD

Number of completers required to accomplish study aims

10

Projected number of subjects who will be enrolled to obtain required number of completers

20

Age range of subject population

18-65

Gender, Racial and Ethnic Breakdown

We plan to enroll 20 participants into the study. Both males and females will be recruited. All eligible participants are accepted; however, past experience with recruitment at STARS suggests that the approximate gender distribution for this study will likely be 20% female and 80% male. Previous and ongoing studies at STARS have had samples comprised of approximately 50% Caucasians, and 50% ethnic minorities distributed as 24% African-American and 22% Hispanic-American, and 4% other. We anticipate a similar representation in this project. We will make every effort to recruit minority patients in order to ensure the generalizability of our findings to the overall treatment population.

Description of subject population

We plan to enroll 20 participants into the study who meet criteria for current AUD.

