## **Criteria for Early Discontinuation**

### Criteria for Early Discontinuation

Drop-out criteria during the screening and study period include:

1. Development of serious psychiatric symptoms as indicated by a CGI improvement score of 6 (much worse than baseline) or greater for 2 consecutive weeks
2. Development of evidence of moderate-to-severe alcohol withdrawal (CIWA-Ar > 13) indicating a need for inpatient detoxification treatment
3. If the participant's continued alcohol use, even if improved from baseline, places him/her at risk for self-destructive behavior or other harm as indicated by a CGI improvement score of 6 (much worse than baseline) or greater for 2 consecutive weeks
4. If the participant becomes pregnant

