#### Describe procedures for minimizing risks

Participants are carefully screened for psychiatric risk prior to admission, so we anticipate the risk of clinically-significant psychological deterioration during participation to be low. The exclusion criteria are designed to minimize the medical and psychiatric risks to participants as discussed above, including risks of adverse events and side effects. All patients will be informed of the possible side effects and risks through extensive discussions with the research psychiatrist during the consent process.

Alcohol withdrawal will be assessed at each study visit using the Clinical Institute Withdrawal Alcohol (CIWA-AR). Anxiety and drinking will be assessed weekly.

Participants will provide a blood sample during screening; they will be warned that blood drawing may cause slight discomfort at the site of needle entry and may result in a small bruise.

Patients are informed prior to study entry that they can refuse to answer any questions and that they can request to stop at any time. If a participant becomes agitated during any of the interviews or assessments, he or she will be provided with therapeutic assistance.

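### Symptom scales are tested by a paired baseline to end-of-study comparison with no rule for a missing end score; read plainly, early leavers drop out and improvement is likely to be overstated

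*Protocol*

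**What the plan says.** The protocol's analysis text for the secondary hypotheses reads: "Paired-samples T tests will be used to compare baseline assessments to end-of-study assessments for continuous variables (e.g., craving or withdrawal scores". Craving and withdrawal are named as examples. Anxiety (HAM-A) and sleep (MOS-Sleep) come under the sentence only because they are continuous scales. The end-of-study assessment is not defined, and no rule covers a participant who lacks one.

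The status of the scales differs. Withdrawal symptoms are listed under Secondary Outcome Measures, although the Design Overview calls them exploratory. Craving, "as measured by the OCDS", is exploratory, as are sleep and anxiety.

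The SAP evaluates drinking and abstinence in each participant's last week on study and tests the change by Wilcoxon signed rank. It lists four drinking variables and does not mention CIWA-Ar, OCDS, HAM-A or MOS-Sleep.

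Under Sample #1, the entry for "Number of completers required to accomplish study aims" is 10, and the entry for "Projected number of subjects who will be enrolled to obtain required number of completers" is 20.

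Two of the Criteria for Early Discontinuation are: "Development of serious psychiatric symptoms as indicated by a CGI improvement score of 6 (much worse than baseline) or greater for 2 consecutive weeks" and "Development of evidence of moderate-to-severe alcohol withdrawal (CIWA-Ar > 13) indicating a need for inpatient detoxification treatment". A third applies the same CGI threshold to harm from continued drinking.

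The section on minimizing risks has CIWA-Ar done at every visit and adds: "Anxiety and drinking will be assessed weekly".

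**The concern.** The protocol's paired t test is the only analysis stated for the symptom scales, and a participant with no end score contributes nothing to it. Some of those absences are produced by rule, when a participant gets worse. The people left in the test would then be a favourable selection, and their mean change would look better than the change in everyone treated.

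The same report would give drinking results for nearly all participants, because each person's last week counts, and symptom results only for those who stayed. A reader could not tell how much of an apparent fall in withdrawal or craving came from who was still there to be measured. HAM-A and CIWA-Ar scores collected before leaving would be unused.

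CIWA-Ar is the most exposed scale. It is named in the protocol's sentence, is listed as a secondary outcome, and is the score that itself triggers removal.

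**Working it through.** **Plan's own figure.** 10 completers from 20 enrolled implies allowance for 50% loss: 10 / (1 - 0.5) = 20, as stated. The documents give no dropout rate, effect size, SD or power for these scales. Everything below about dropout is therefore an assumption, in SD units of the change score.

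**Step 1: size of the bias in general.** With completer share c,

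bias = (1 - c) x (mean improvement in completers - mean improvement in leavers).

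| Gap between completers and leavers | c = 0.5 | c = 0.8 |
|---|---|---|
| 0 | 0 | 0 |
| 0.25 SD | 0.125 | 0.05 |
| 0.50 SD | 0.25 | 0.10 |
| 1.0 SD | 0.50 | 0.20 |

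**Step 2: simulation with no true change.** Mid-trial and end changes are bivariate normal with correlation 0.3, 0.5 or 0.7. The participants with the worst mid-trial score plus noise (noise SD 0, 1 or 2) leave. A paired t test is run on those who remain. The nominal chance of a significant result in the favourable direction is 2.5%.

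| Assumption | False improvement | Favourable significant result |
|---|---|---|
| Leaving unrelated to score | 0 SD | 2.5% |
| 10 leave, full range of the nine cases | 0.10 to 0.54 SD | 5% to 44% |
| 10 leave, correlation 0.5, noise SD 1 (central case) | 0.27 SD | 12-13% |
| 4 leave, otherwise as the central case | 0.12 SD | 7% |

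**Step 3: a different dropout model.** Here the chance of completing depends on the end change itself, with 50% completing on average. If the log-odds of completing rise by 0.5, 1 or 2 per SD of improvement, the bias is 0.24, 0.42 or 0.61 SD, and a false improvement is declared in 10.5%, 24.8% or 56.5% of trials. If improvers are the ones who leave (slope -0.5), the bias is -0.24 SD, an understatement.

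**Step 4: what adjustment does.** In the Step 2 setting, regressing the end change on the mid-trial score (a stand-in for the mixed model) removes the bias in all nine cases. It does so because leaving there depends on a recorded score. It does not buy precision: in the central case the SD of the estimate rises from 0.31 to 0.37.

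**Step 5: precision.** Two-sided 5%, 80% power, paired t: the detectable change is 1.00 SD with 10 pairs and 0.66 SD with 20. The 95% half-widths are 0.72 and 0.47 SD. This is the cost of losing half the end scores, and no analysis method recovers it in full.

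**The case against.** The strongest reply is that the protocol does not choose a completers-only analysis; it leaves the end point undefined. End-of-study could mean week 8, the post-taper visit in week 10, or the last on-study score, which is what the SAP uses for drinking. That is fair as far as it goes. But the SAP wrote its last-week rule for drinking and abstinence alone, and a fixed end visit is the plainer reading elsewhere. Either way the SAP needs to say.

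Three further objections stand in part:

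- Ten is a required minimum, not a forecast. A reader might infer that half the sample will be lost; the documents support only that as few as half may contribute.
- Leavers may go because of side effects, for unrelated reasons or because they are better. No removal rule is triggered by OCDS, HAM-A or MOS-Sleep, and the protocol reports that nobody in the gabapentin pilot was removed for alcohol withdrawal. A reader might infer that overstatement is established; the documents make it likely, because the outcome-based removal rules point one way, but do not prove it.
- This is an open-label, single-arm pilot with dose and tolerability as primary outcomes. No p-value on these scales could establish efficacy.

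It may also be said that extending the last-week rule to these scales would be simpler. It would keep most leavers in, but it would mix scores from different weeks and so would not estimate change at week 8.

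**Conclusion.** The concern holds conditionally. If the test is applied as plainly written, participants without an end score are excluded, as few as 10 of 20 contribute, and improvement in withdrawal, craving, anxiety and sleep is likely to be overstated. The plausible range under assumed mid-trial dropout is 0 to about 0.5 SD, with a favourable false-positive rate of 2.5% to 44%; the central case is 0.27 SD and 12-13%. These figures depend on how many leave and why, which the documents do not say, and the sign could reverse.

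A reader might also take the ratio of standard errors, sqrt(20/10) = 1.41, as the gain from changing the analysis. It is not: the mixed model addresses selection, and its interval may be wider than the completers' interval.

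Only secondary and exploratory results are affected. The change is worth making because the interim HAM-A and CIWA-Ar scores are already planned.

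**What to change.** In the SAP:

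1. Define the end time point for the symptom scales as on-treatment week 8.
2. Analyse CIWA-Ar and HAM-A, and OCDS and MOS-Sleep where they are repeated, with a linear mixed model on all post-baseline scores to week 8: week as a factor, a random participant intercept, and the baseline score included. For CIWA-Ar, state how several scores in one week are reduced to one.
3. Report the week-8 change with a 95% interval and the number contributing at each week, and say how many had no post-baseline score.
4. Keep the paired t test, labelled as a completers-only check.

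The assessment schedule is a separate attachment, so how often OCDS and MOS-Sleep are given must be confirmed first. If a scale is measured only at baseline and the end, the model adds nothing, and the paired result should be reported with the number analysed and that limitation.

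The cost is SAP wording and a PROC MIXED run in SAS, which the SAP already names; no new data are needed. The downsides are that the model assumes leaving is explained by recorded scores, so it would not repair the dropout in Step 3, and that its interval may be wider than the completers' interval.

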## Uploads

Upload the entire grant application(s)

Upload copy(ies) of unbolted Consent Form(s)

pregab-AUD cf unbolted 5-9-17.pdf

Upload copy(ies) of bolted Consent Form(s)

Upload copy(ies) of the HIPAA form

PP2PDFPrepUEAuthorization 4-18-17.pdf

Upload any additional documents that may be related to this study

7491\_FB\_prov\_app\_memo\_05-10-17.pdf

pregabalin IND exemption.pdf

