Study: AN OPEN-LABEL PILOT STUDY OF PREGABALIN AS TREATMENT FOR ALCOHOL USE DISORDERS

PI: [name]

IRB: 7491

NCT#: NCT03256253

Data Analysis Plan created 6-28-2017

Statistical Analyses

Summary statistics of baseline demographics of the sample will be computed using frequencies, means and standard deviations. For skewed distributions, medians and interquartile ranges (IQR) will be computed. Study retention will be summarized using proportions and by computing the mean number of weeks in the trial completed.

For the primary outcome measure, the maximum maintained dose will be reported with mean and standard deviation. For measures of drinking and abstinence for each participant it will be computed during the participant's last week of study participation: proportion of heavy drinking days, proportion of abstinent days, number of drinks per week, and number of drinks per drinking day. The same measures will be computed at baseline using the weekly average over the past 28 days. Wilcoxon signed rank tests will be used to analyze the change from baseline to the last week of study participation. Side effects will be summarized by creating indicators of whether subjects reported: any side effects during the trial, any dose reductions due to side effects, and any discontinuation of medication due to side effects. All analyses will be conducted in SAS® (version 9.4) and all statistical tests were 2-tailed at a significance level of 5%.

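### The protocol's chi-square test does not fit two paired drinking outcomes; the SAP's signed rank test does, but neither precedence nor one end window is stated

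*Protocol*

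**What the plan says.** **Protocol, Hypotheses testing.** For the secondary hypotheses, scores measured on a scale get a paired test: "Paired-samples T tests will be used to compare baseline assessments to end-of-study assessments for continuous variables (e.g., craving or withdrawal scores". The two drinking outcomes get a chi-square instead, which is to "be used for variables reported as proportions (e.g., percent days abstinent, proportion heavy drinking days". Pairing is named for the t test only. No table layout, unit of analysis or window is given for the chi-square.

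**SAP, Statistical Analyses.** Four drinking measures are taken in each participant's last week in the study: "proportion of heavy drinking days, proportion of abstinent days, number of drinks per week, and number of drinks per drinking day". For baseline, "The same measures will be computed at baseline using the weekly average over the past 28 days". Then: "Wilcoxon signed rank tests will be used to analyze the change from baseline to the last week of study participation". Tests are two-sided at 5%. Withdrawal and craving are not mentioned.

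**End point in time.** The protocol (Hypotheses testing; Study Procedures, Design Overview) compares baseline with the study end, without saying which week that is. The SAP uses each participant's own last week.

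**Dates.** The SAP is headed "Data Analysis Plan created 6-28-2017". The protocol's own date is not in the text supplied, but its Uploads section lists a consent form named "pregab-AUD cf unbolted 5-9-17.pdf". Nothing in the supplied text says which document prevails.

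**The concern.** With one arm, every drinking result compares a person with himself or herself. The protocol recognises this for continuous scores but not for the two drinking outcomes, which are also within-person comparisons. An ordinary chi-square assumes independent yes/no observations. Percent days abstinent and proportion of heavy drinking days are neither independent across periods nor yes/no per person. A paired (McNemar) version would need a binary outcome per person, which the protocol does not define.

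Three things are at stake, all outside the primary outcomes:

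- the error rate of two secondary results, if the protocol's sentence were followed;
- whether people who leave early count in the comparison;
- whether one supplementary SAP measure drops complete responders without saying so.

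**Working it through.** **1. Figures to reproduce.** Neither document gives power, an effect size or an SD for these outcomes. The only arithmetic is 10 completers from 20 enrolled (Description of Subject Population): 10 / (1 − 0.50) = 20, where the 50% is merely implied.

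**2. Chi-square on pooled person-days.** This is one reading of the protocol, not a stated plan. Let each person's true daily rate have mean m and between-person variance τ² in both periods, with correlation ρ between periods and no mean change. With k₀ baseline days and k₁ end days per person, put h = 1/k₀ + 1/k₁.

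- Variance the chi-square assumes for the difference in pooled proportions: m(1 − m)h / n
- Actual variance: {[m(1 − m) − τ²]h + 2τ²(1 − ρ)} / n
- Ratio: R = 1 + τ²[2(1 − ρ) − h] / [m(1 − m)h]
- Rejection rate at nominal 5%: about 2[1 − Φ(1.96/√R)]

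R does not depend on n. The test is conservative when 2(1 − ρ) < h and anti-conservative otherwise. For 28 v 7 days, h = 1/28 + 1/7 = 0.1786, so the switch is at ρ = 1 − 0.0893 = 0.91. For 7 v 7 days, h = 0.2857 and the switch is at ρ = 0.86.

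Worked case (assumption): heavy-day rates uniform on 4/7 to 1. The lower limit is the entry criterion of 4 days a week. Then m = 11/14 = 0.786, τ² = (3/7)²/12 = 0.0153 and m(1 − m) = 0.1684. For 28 v 7 days and ρ = 0.5, R = 1 + 0.0153 × (1 − 0.1786) / (0.1684 × 0.1786) = 1.42, so the rejection rate is 2[1 − Φ(1.96/1.191)] = 10.0%.

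The simulation used heavy-day rates on 4/7 to 1 and abstinence rates on 0 to 3/7, uniform or truncated beta, n = 10 and 20, 20,000 replicates per setting. Its correlations are on the Gaussian-copula scale.

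| ρ | 28 v 7, formula | 28 v 7, simulated | 7 v 7, formula | 7 v 7, simulated |
|---|---|---|---|---|
| 1.0 | 4.0% | 3.6–4.4% | 4.0% | 3.6–4.2% |
| 0.8 | 6.3% | 6.5–7.4% | 5.4% | 5.2–6.1% |
| 0.5 | 10.0% | 9.9–12.3% | 7.7% | 7.8–9.3% |
| 0.3 | 12.4% | 12.1–15.5% | 9.2% | 9.1–11.2% |

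The formula column is for the uniform heavy-day case only.

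**3. Other readings and the SAP's test.** An unpaired chi-square on a yes/no per person (true rate above the middle of the eligible range) rejects 0.0–3.4% under the same assumptions. The signed rank test with 28 v 7 days rejects 3.4–6.4%. A second simulation, not confined to the entry range (mean rate 0.6, beta precision 4, SD of individual change 0 to 2 on the logit scale), gave about 3% to 28% for the pooled chi-square and 4.4–5.1% for the signed rank test.

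**4. End window.** Read literally, a study-end comparison could rest on about 10 people, while the last-week comparison can use up to 20. As a yardstick only, a paired t test with 80% power (two-sided 5%) detects a change of 1.00 SD with 10 people and 0.66 SD with 20. For completers the SAP's last week is itself unclear. Study Visits describes an 8-week period, one visit in taper week 9 and a post-taper visit in week 10. Compensation says the week 9 visit completes the week 8 data.

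**5. Drinks per drinking day.** With no drinking day in the last week the measure is 0/0. If 10–40% of people are abstinent that week (assumption), 2–8 of 20, or 1–4 of 10, have no value. Unless one is imputed, they leave the paired test.

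**6. Outcome status and direction.** Withdrawal is secondary under Secondary Outcome Measures and exploratory in the Design Overview. Percent days abstinent is secondary in both places but appears again in the exploratory list, as do heavy drinking days. The secondary list predicts that abstinent days will fall, against the aim of promoting abstinence in the Lay Summary.

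**The case against.** The strongest reply is that the problem is already solved. The SAP is the dedicated analysis document, is dated after the protocol's dated uploads, and gives a paired test, both windows, the level and the sidedness for the same two outcomes. This largely stands. The documents also complement each other on withdrawal and craving, where only the protocol names a test. But for that reason the protocol's paragraph cannot simply be treated as superseded: someone must say which half survives.

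A reader might infer that the planned analysis has an inflated false-positive rate. The documents do not support that. The protocol gives no layout for its chi-square, and the direction of the error changes with the layout. The 28 v 7 day figures join the protocol's test to windows that appear only with the SAP's test. The simulation behind the 4–16% range also holds end-of-treatment rates within the entry range, although that criterion covers only the 28 days before entry.

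A reader might also infer that the protocol excludes dropouts. No section restricts the drinking analysis to completers, the 10 is a recruitment figure, and the SAP's window can be read as making an undefined study end operational. Neither document assigns a paired t test to the drinking outcomes, so the 1.00 v 0.66 SD contrast shows scale only.

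On status, the exploratory entry for heavy drinking days may be a count rather than a repeat of the proportion. The SAP gives the drinking measures no tier, so it does not contradict the protocol's tiers. No multiplicity scheme depends on them.

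**Conclusion.** The point holds as a defect in the protocol's wording and a gap between the two documents. No version of the chi-square fits these outcomes as defined. Its error rate could be under or over 5%: illustratively 0–3% or 4–16%, under no true change, rates within the entry range and the layouts shown. The SAP's signed rank test is sound and probably governs, but this is an inference from its date and detail.

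The undefined study end and the 0/0 measure are real gaps. The share of people affected by the second is unknown, and 10–40% is an assumption. The status and direction items are editorial and change no test and no two-sided p-value. The primary outcomes, dose and tolerability, are untouched. Overall severity is minor to moderate. Confidence is high on the textual mismatch and low on any single error-rate figure.

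**What to change.** 1. In Hypotheses testing, replace the chi-square for percent days abstinent and proportion of heavy drinking days with the SAP's Wilcoxon signed rank test.
2. State that the SAP governs the drinking outcomes and that the protocol's paired t test stands for withdrawal and craving.
3. Use the SAP's last-week window for the drinking outcomes throughout. Say which week it is for completers (week 8, taper week 9 or post-taper week 10), and which assessment is the end value for withdrawal and craving.
4. Report drinks per drinking day descriptively among last-week drinkers, with the number of abstainers shown. Keep drinks per week as the tested quantity measure.
5. Editorial: give withdrawal one status; remove percent days abstinent from the exploratory list; say whether heavy drinking days there is a count; in Secondary Outcome Measures, change lower to higher for percent days abstinent.

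The cost is wording in both documents, with no added data, visits or patient burden. The one loss is a tested supplementary measure.
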